## Analysis Plan

Statistical models

To test Hypotheses 1a /1b/1c/1d, we will use a binomial logistic regression analysis. The two categorical independent variables will be 'total survival displayed' and 'stratified transplant survival'; the model will also include an interaction term of these two variables. The dependent variable is binary choice of hospital. -We will test whether the main effect of "total survival displayed" is statistically significant and in the predicted positive direction. -We will test whether the main effect of "stratified transplant survival" is statistically significant and in the predicted positive direction. -We will test whether the interaction effect "total\*stratified" is statistically significant in the predicted negative direction. To test Hypothesis 2, we will conduct a causal mediation analysis to determine whether information display had a mechanistic effect on hospital choice through our proposed mediator. We will estimate the average causal mediation effect (ACME), average direct effect (ADE), and the total effect. The ACME is the effect of each information display condition (total, stratified, or total\*stratified) on the outcome of hospital choice (selective vs. non-selective), mediated through the hypothesized mediator (the importance of "getting any heart" at each hospital when considering the choice). The remaining effect of information display on hospital choice that is not mediated through the hypothesized mediator represents the ADE. The entire effect of the information display on hospital choice via the hypothesized mediator and the direct effect is the total effect. The proportion of the total effect that is accounted for by the ACME is called the proportion mediated.{Imai, 2010}. Analyses will be performed using the "mediation" package in R (The R Foundation for Statistical Computing).{Tingley, 2014}. We will generate 95% confidence intervals by using 1000 bootstrap simulations. The unstandardized point estimate of the ACME and its 95% confidence intervals will be interpreted. -A significant ACME for "total survival displayed" would suggest that displaying total survival works via increasing the perceived importance of "getting any heart" to increase preference for the non-selective hospital. If the ACME is non-significant, we will identify where the causal path breaks down. -A significant ACME for "stratified transplant survival" would suggest that stratifying transplant survival by number and quality of accepted donors works via increasing the perceived importance of "getting any heart" to increase preference for the non-selective hospital. If the ACME is non-significant, we will identify where the causal path breaks down. -A significant ACME for "total survival displayed\*stratified transplant survival" would suggest that the combination of displaying total survival and stratifying transplant survival by number and quality of accepted donors works via increasing the perceived

importance of "getting any heart" to increase preference for the non-selective hospital. If the ACME is non-significant, we will identify where the causal path breaks down. To test Hypothesis 3, we will use a binomial logistic regression analysis with a contrast test for a difference in effect size between conditions 4 and 5.

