## Hypotheses

Hypothesis 1: When centers must present information on their transplant success rate only, lay evaluators will respond by selecting hospitals with higher transplant success. However, if information presented on transplant outcomes is stratified by the number and quality of donors used, or displayed in addition to total survival rates, then participants will respond by selecting hospitals with higher organ acceptance rates rather than the hospital with higher transplant outcomes. Hypothesis 1a: Preference for the non-selective transplant center will be lower (than for the selective center) in condition 1 (baseline: combined transplant survival only), compared to the other 4 conditions. That is, a higher proportion of participants will prefer the non-selective center over the selective center in conditions 2, 3, 4, and 5, relative to condition 1. Hypothesis 1b: There will be a main effect of viewing total survival, such that in conditions 2 and 4 (when total survival is displayed), participants will prefer the non-selective center over the selective center, relative to the baseline condition 1. Hypothesis 1c: There will be an additional main effect of viewing stratified transplant survival, such that in conditions 3 and 4 (when transplant survival is stratified by number and quality of donor hearts accepted at each center) participants will prefer the non-selective center over the selective center, relative to the baseline condition 1. Hypothesis 1d: There will be an interaction effect between total and stratified transplant survival, such that when participants view both stratified transplant survival and total survival outcomes together, preference for the non-selective center is higher relative to preferences at baseline (condition 1), but not higher relative to preferences when total survival information is added to the display (condition 2) or stratified transplant survival

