## Variables

Manipulated variables

We will manipulate how transplant center outcomes are presented. Different components of the same outcome statistics for two transplant centers will be varied over five different conditions. (1) Condition 1 ("baseline" condition): view only combined transplant survival (e.g. transplant survival rate not stratified by number and quality of donor hearts accepted at each center) (2) Condition 2: view combined transplant survival + total survival (e.g. overall survival rate at each center, computed from survival rates of both transplant and waitlist patients) (3) Condition 3: view only stratified transplant survival (e.g. transplant survival rate stratified into patients who received excellent donor organs and patients who received less than optimal donor organs) (4) Condition 4: view stratified transplant survival + total survival (5) Condition 5: view only total survival The first four conditions (1-4) will be included in our main analysis, which is a 2x2 design with 2 factors (total survival and transplant survival) and 2 levels per factor: (i) Total survival: "total not displayed" = reference level, in which only transplant survival rate (and no total or waitlist survival) is shown "total displayed" = transplant survival is displayed along with the overall survival rate at each center, which is computed from survival rates of both transplant and waitlist patients (ii) Transplant survival: "combined": reference level, in which transplant survival rate is not stratified by number and quality of donor hearts accepted at each center "stratified": transplant survival rate stratified into patients who received excellent donor organs and patients who received less than optimal donor organs The additional fifth condition, in which only total survival outcomes (and no transplant survival outcomes) are displayed, will be included in the study and analyzed separately.

Measured variables

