#### *No files selected*

##### Transformations

Logistic regression analysis: The categorical predictor "total survival displayed" will be dummy coded (0=not displayed, 1=displayed), with 'not displayed' as the reference category. The categorical predictor "transplant survival stratified" will be dummy coded (0=not stratified, 1=stratified), with 'stratified' as the reference category. The outcome variable "choice of hospital" will be dummy-coded (0=selective hospital, 1=non-selective hospital). The reference category is 'selective hospital'. Mediation analysis: The categorical predictor "total survival displayed" will be dummy coded (0=not displayed, 1=displayed), with 'not displayed' as the reference category. The categorical predictor "transplant survival stratified" will be dummy coded (0=not stratified, 1=stratified), with 'stratified' as the reference category. The categorical interaction term "total survival displayed\*transplant survival stratified" will be dummy coded (0=total and stratified information not displayed together, 1=both total and stratified information displayed together), with 'both' as the reference category. The continuous mediator variable "get any heart" will be mean-centered for each analysis. The outcome variable "choice of hospital" will be dummy-coded (0=selective hospital, 1=non-selective hospital). The reference category is 'selective hospital'.

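### The listed H1 tests compare conditions 2 and 3 with baseline but never condition 4, although H1a to H1d all claim that condition 4 exceeds baseline

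*Combined protocol and SAP*

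**What the plan says.** All four parts of Hypothesis 1 (Hypotheses section) place condition 4 above condition 1:

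- H1a: conditions 2, 3, 4 and 5 each exceed condition 1.
- H1b: "There will be a main effect of viewing total survival, such that in conditions 2 and 4" preference for the non-selective center is higher than at baseline.
- H1c: "There will be an additional main effect of viewing stratified transplant survival, such that in conditions 3 and 4" the same holds.
- H1d: condition 4 is above condition 1 but not above condition 2 or condition 3.

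For all of these, Statistical models specifies a single binomial logistic regression on the two factors, and "the model will also include an interaction term of these two variables". Three tests follow. The first reads "We will test whether the main effect of 'total survival displayed' is statistically significant and in the predicted positive direction", the second is its counterpart for stratification, and the third looks for a significant negative interaction. The only contrast between conditions named anywhere in the plan is 4 versus 5, for Hypothesis 3.

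Under Transformations the total-survival factor "will be dummy coded (0=not displayed, 1=displayed), with 'not displayed' as the reference category". The stratification factor "will be dummy coded (0=not stratified, 1=stratified), with 'stratified' as the reference category". That second statement conflicts with its own 0/1 codes. It also conflicts with Study design and Manipulated variables, which both make the combined (not stratified) display the reference level.

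**The concern.** In a dummy-coded model with a product term, the coefficient of one factor is its effect when the other factor is at its reference level. It is a simple effect between two cells, not a main effect over the 2x2 table. The tests labelled as main effects therefore say nothing about condition 4, while the hypotheses they are meant to decide do. The study could report two significant positive main effects and a significant negative interaction, as predicted, when the combined display does no better than baseline. A reader would naturally take that result as support for H1b, H1c and H1d, including their statements about condition 4.

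**Working it through.** **Inputs.** Rates of 45% and 60%, 90% power and alpha 0.05 come from Sample size rationale, and about 200 per condition from Sample size. The plan does not state sidedness; two-sided 0.05 with the predicted direction required is assumed here. The condition 4 rates below other than 60% are illustrative assumptions.

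**The plan's own figure first.** Pooled-variance normal approximation, 200 versus 200, 45% versus 60%:

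- Null SE = sqrt(2 x 0.525 x 0.475 / 200) = 0.0499.
- Alternative SE = sqrt((0.45 x 0.55 + 0.60 x 0.40) / 200) = 0.0494.
- Two-sided power = Phi((0.15 - 1.96 x 0.0499) / 0.0494) = 85.4%.
- One-sided power = 91.5%.
- Two-sided, 200 versus the other 800 pooled: 96.9%.

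The stated 90% is thus reached one-sided or against the pooled conditions, but not for a two-sided pairwise comparison.

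**What each coefficient is.** Let L1 to L4 be the log-odds of choosing the non-selective hospital in conditions 1 to 4, with not displayed and not stratified coded 0:

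- b_total = L2 - L1
- b_strat = L3 - L1
- b_int = L4 - L3 - L2 + L1
- condition 4 versus 1 = L4 - L1 = b_total + b_strat + b_int

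L4 appears in neither of the first two lines. This is algebra and needs no assumed rates.

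**Worked table.** Take 90, 120, 120 and 90 of 200 in conditions 1 to 4 (45/60/60/45%):

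- b_total = b_strat = 0.405 - (-0.201) = 0.606; SE = sqrt(1/90 + 1/110 + 1/120 + 1/80) = 0.203; p = 0.0028 each.
- b_int = -1.212, SE 0.286, p = 0.00002.
- 4 versus 1 = 0.606 + 0.606 - 1.212 = 0.000, SE 0.201, p = 1.0.

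All three listed tests succeed, although condition 4 equals baseline.

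**How often this happens.** Simulation, 400,000 replicates, 200 per cell, Wald tests, conditions 1 to 3 at 45/60/60%:

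| Condition 4 rate | Both coefficients positive | Negative interaction | All three listed tests | 4 vs 1 positive |
|---|---|---|---|---|
| 40% | 77% | 99.9% | 77% | 0.1% |
| 45% | 77% | 99% | 77% | 2.5% |
| 50% | 77% | 95% | 76% | 17% |
| 60% | 77% | 56% | 53% | 86% |
| 73% (no interaction) | 77% | 2.5% | 2.5% | >99% |

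The second column does not move, because condition 4 is not in it. The interaction test moves the wrong way to act as a safeguard: it succeeds more often as condition 4 gets worse.

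**Mediation.** Statistical models interprets the mediated effect (ACME) for the total-by-stratified term as that of showing both displays. The plan does not say whether the three terms enter jointly. If they do, the term is the departure from additivity. If it is entered alone in conditions 1 to 4, it compares condition 4 with conditions 1 to 3 pooled. Neither is condition 4 versus 1.

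**The case against.** Several points on the other side stand.

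- H1b and H1c are worded relative to condition 1, so baseline-referenced simple effects are the right tests for their condition 2 and condition 3 parts. Only the condition 4 part is untested, and since the model is saturated that contrast is a sum of fitted coefficients.
- A reader might infer that the three tests can establish the whole of Hypothesis 1. The plan never says that they jointly do so. H1a also covers condition 5, which lies outside the 2x2 model, so they could not settle H1a under any coding.
- A reader might take 77% as the expected rate of false conclusions. It is not. The 45/60/60/45% pattern is an assumed worst case in which two displays each add 15 points and together add nothing, and nothing in the documents suggests it. Under 45/60/60/60%, all three tests succeed without a significant 4 versus 1 in about 6% of trials (53.4% - 47.4%).
- The reference-level statement might be read to mean that the total-survival test is really condition 4 versus 3. Taken literally it would be, but the printed codes and two other sections point to a wording slip. At 45/60/60/60% conditions 3 and 4 are equal, so the roughly 5% two-sided rejection rate for that comparison is type I error, not low power.

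None of this supplies the missing test. That 4 versus 1 can be derived from the fit does not make it prespecified, and no hypothesis is made to depend on it.

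**Conclusion.** The concern holds for condition 4. The listed tests correctly address 2 versus 1 and 3 versus 1, but none addresses 4 versus 1, which H1a, H1b, H1c and H1d all assert. This is a mismatch between the stated tests and the stated hypotheses in the main analysis, not merely missing detail. Its core is algebraic and rests only on the printed 0/1 codes and the product term.

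The size is illustrative and depends on about 200 per cell, two-sided 0.05 and the assumed rates. The listed tests succeed together more often when condition 4 is no better than baseline (about 77%) than under the hypothesised 45/60/60/60% (about 53%). The documents do not support the stronger reading that the two coefficients are invalid tests. Whether the sample size delivers 90% power is a separate matter.

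**What to change.** 1. In Statistical models and Transformations, call the two coefficients simple effects (2 versus 1, 3 versus 1). Correct the reference level of the stratification factor to not stratified, in line with its codes and with Study design and Manipulated variables.
2. Prespecify condition 4 versus 1 as b_total + b_strat + b_int from the same model, and make the condition 4 parts of H1a to H1d depend on it: H1b needs 2 versus 1 and 4 versus 1; H1c needs 3 versus 1 and 4 versus 1.
3. Add a 5 versus 1 test for H1a. For H1d, report 4 versus 2 (b_strat + b_int) and 4 versus 3 (b_total + b_int) with confidence intervals, since a non-significant difference does not show that condition 4 is not higher.
4. In the mediation analysis, define the combination ACME as condition 4 versus condition 1.

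Averaged main effects from -0.5/+0.5 coding could be reported as well, but they do not replace these contrasts: each has about 56% power at 45/60/60/60%.

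The cost is wording and a few contrasts, mostly from a model already planned, with no extra participants. There is a real price in power. Requiring both 2 versus 1 and 4 versus 1 lowers H1b power from about 86% to 77% at 45/60/60/60%, so the chance of missing it rises from about 14% to 23%.

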### Randomization

We will use simple randomization, where each participant will be randomly assigned to one of the five predetermined conditions. The Qualtrics randomizer function will be used for randomization into a condition.

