### Sample size

Our target sample size is 1000 participants. We expect that this will amount to approximately 200 participants per condition, although due to the nature of the randomization technique used (Qualtrics randomizer function), we may end up with slightly more or slightly less than 200 per condition.

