### Sample size rationale

Sample sizes were calculated to yield at least 90% power to detect a 15 percentage point difference (e.g., 45% vs. 60%) between baseline condition 1 and the other 4 conditions, with  $\alpha=0.05$  (GPower 3.1.9.4).

Stopping rule

Participants will be recruited until a sample size of 1000 is achieved.

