The outcome variable will be a binary choice between two hospitals: one with a selective donor-heart acceptance strategy and one with a non-selective donor heart acceptance strategy. Participants will respond to the question "Which Hospital is a better choice for patients? Please click on one of the two tables below to indicate which hospital is the better choice." Participants will choose between two outcome tables featuring the selective and non-selective hospital (counterbalanced, such that each of the two choices is equally likely to be presented at top of the choice scenario in each condition). The number of participants that choose each hospital will be the measured outcome variable used in analyses. On the next page of the survey, participants will respond to three mediator questions: "There are many reasons why one transplant hospital might outperform another. Which reasons were most important in your decision? Please move the slider to indicate how much you considered each of the reasons below (0=reason was not important, 100=reason was extremely important)." Participants will then move a slider bar (0-100) to indicate the importance of the following three items: (1)

Patients were more likely to receive an excellent donor heart at the hospital I picked. (2) Patients were less likely to receive a marginal donor heart at the hospital I picked. (3) Patients were more likely to receive any kind of heart at the hospital I picked. The third item (more likely to receive any kind of heart) will be the only variable that is included in the planned mediation analysis.

Indices

*No response*

*No files selected*

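### A significant ACME is read as mechanism, although the rating is not randomised and follows the choice; if the display moves the rating, an unmeasured shared cause can produce one with no mediation

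*Combined protocol and SAP*

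**What the plan says.** The Analysis Plan (Statistical models) sets the aim for Hypothesis 2: "we will conduct a causal mediation analysis to determine whether information display had a mechanistic effect on hospital choice through our proposed mediator". It plans the ACME, the average direct effect, the total effect and the proportion mediated, with 95% intervals from 1000 bootstrap simulations. A significant ACME for total survival "would suggest that displaying total survival works via increasing the perceived importance of" getting any heart. The same reading is given for stratified survival and for the combination. A non-significant ACME is also read causally, as a prompt to find where the path fails.

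Only the display is randomised: under Randomization, "each participant will be randomly assigned to one of the five predetermined conditions". Under Measured variables, the choice comes first. The 0-100 sliders follow on the next page, and the only item used as mediator is "Patients were more likely to receive any kind of heart at the hospital I picked".

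The plan names no covariates for the mediation models, does not state that rating and choice must share no unmeasured cause, and has no sensitivity analysis for that assumption. The one repeat analysis, restricted to those who pass both attention checks (Data exclusion), deals with data quality. Exploratory analysis is left blank.

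**The concern.** Randomisation protects the total effect of the display and its effect on the rating. It does not protect the link between rating and choice, which is observational. The ACME combines the protected link with the unprotected one. It is causal only if, within condition, rating and choice share no unmeasured cause and the rating comes before the choice. The plan states neither condition, and its own order of questions breaks the second.

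A trait such as numeracy, or care in reading the introduction (examples of mine, not the documents'), could affect both the rating and the choice. If the display also moves the rating, the product of the two links differs from zero and the planned reading reports a mechanism that may not exist. Hypothesis 2 itself predicts that the rating will be lower in condition 1 than in conditions 2-4, so a shift in the rating is the study's own working case. At stake is what may be concluded about why displays change choices.

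**Working it through.** **Inputs from the documents.** Sample size: "Our target sample size is 1000 participants", with "approximately 200 participants per condition". Choice rates of 45% and 60% are the example under Sample size rationale. Alpha is 0.05.

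**Inputs assumed.** The documents give no SD for the rating, no expected shift and no residual correlation. Shifts d of 0 to 0.5 SD and residual correlations rho of 0 to 0.3 are used. A rho of 0.1 corresponds to one unmeasured cause explaining 10% of the residual variance of the rating and 10% of that of the latent choice. The true effect of rating on choice is set to zero.

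**The plan's own figure.** It claims "at least 90% power to detect a 15 percentage point difference". For 200 against 200, the SE under the alternative is sqrt(0.45×0.55/200 + 0.60×0.40/200) = 0.0494, and the SE under the null is sqrt(2×0.525×0.475/200) = 0.0499. One-sided: (0.15 − 1.645×0.0499)/0.0494 = 1.37, power 91.5%. Two-sided: (0.15 − 1.96×0.0499)/0.0494 = 1.06, power 85.4%. Two-sided, 200 against 800 pooled: 96.9%. The claim therefore reproduces one-sided or pooled. It concerns Hypothesis 1; the plan gives no figure for mediation.

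**False ACME from a shared cause.** A product of two paths is significant roughly when both paths are, so P(false ACME) ≈ P_a × P_b.

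- Display to rating: z_a = d × sqrt(200/2) = 10d, and P_a = Φ(z_a − 1.96) + Φ(−z_a − 1.96).
- Rating to choice: splitting the latent choice into two shrinks rho by φ(z_p)/sqrt(p(1 − p)), where z_p is the normal quantile of p. This is 0.796 at 45% and 0.789 at 60%, mean 0.792. Then z_b = 0.792 × rho × sqrt(400) = 15.8 × rho, which is 1.58, 3.17 and 4.75 at rho 0.1, 0.2 and 0.3. P_b = 0.354, 0.887 and 0.997.

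Each cell gives formula / simulation. The simulation uses a linear rating model, a logistic choice model and a Monte Carlo 95% interval for the product, with 1,500 runs per cell for 0.3-0.5 SD and 600 for 0.1-0.2 SD.

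| Shift (SD) | P_a | rho 0.1 | rho 0.2 | rho 0.3 |
|---|---|---|---|---|
| 0.1 | 0.170 | 6% / 5% | 15% / 13% | 17% / 19% |
| 0.2 | 0.516 | 18% / 18% | 46% / 45% | 51% / 48% |
| 0.3 | 0.851 | 30% / 28% | 75% / 75% | 85% / 85% |
| 0.4 | 0.979 | 35% / 33% | 87% / 86% | 98% / 98% |
| 0.5 | 0.999 | 35% / 35% | 89% / 90% | 100% / 100% |

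At rho 0 the simulated rate is 4-5% for shifts of 0.3-0.5 SD. With no shift it is at most 6% for every rho up to 0.5. P_a is in effect the ceiling: a shared cause cannot inflate the ACME beyond the chance of detecting the display's effect on the rating.

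**Larger sample.** The plan does not say whether each ACME uses two conditions or all four. With 800 participants and a 10-point shift on an assumed SD of 25 (0.4 SD), the rate is 58% at rho 0.1 and 99% at 0.2 (500 runs). A check with 1000 bootstrap resamples, as the plan intends, gave 68% and 100% (60 runs; standard error about 6 points for the first).

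**Size of the spurious effect.** In that setting the mean ACME is 1.54, 3.17 and 4.65 percentage points at rho 0.1, 0.2 and 0.3. Divided by the 15-point total effect, that is 10%, 21% and 31% mediated, when the true value is zero.

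**Reverse order.** Let the choice alone shift the later rating by c points (SD 25), with no mediation and no shared cause. With 800 participants, a false ACME appears in 39% of trials at c = 20 and 77% at c = 40. The rho needed to bring that ACME to zero is the within-condition biserial correlation. With k = c/25 and q = 1 − p, it is [k sqrt(pq)/sqrt(1 + k²pq)] × sqrt(pq)/φ(z_p). At p = 0.45, where sqrt(pq) = 0.4975 and φ(z_p) = 0.3958:

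- c = 10: 0.195 × 1.257 = 0.25 (simulated 0.24)
- c = 20: 0.370 × 1.257 = 0.46 (simulated 0.47)
- c = 40: 0.623 × 1.257 = 0.78 (simulated 0.78)

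The more the choice drives the rating, the more robust the ACME would look.

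**The case against.** The wording is already hedged: the plan says a result would suggest, and calls the mediator putative or hypothesised. It will also interpret the point estimate and interval, not significance alone, and a spurious 1.5 percentage points at rho 0.1 would look small. This softens the point. But the stated purpose is to determine a mechanistic effect, and no condition is attached to the reading.

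A reader might infer that any modest shared cause yields a false mechanism, or that the error rate is very high even under a small correlation. Neither is supported. Inflation needs the display to move the rating, and the documents give no size for that movement. At rho 0.1 and 200 per arm the rate is about 30-35% even for shifts of 0.3-0.5 SD; the very high rates need rho of 0.2 or more.

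The strongest objection is to the remedy. A sensitivity analysis over rho takes the rating to precede the choice, and here it does not, so a large break-even rho could reassure falsely. That objection stands, and the analysis is worth adding only if the order is acknowledged beside it. It is also tempting to accept mediation whenever the true residual correlation lies below the break-even value. That rule cannot be applied, because the true rho cannot be estimated from these data.

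**Conclusion.** The point holds, limited to Hypothesis 2. As planned, a significant ACME cannot separate mediation from a shared cause of rating and choice, or from the choice shaping the later rating. The false-positive rates for a shared cause depend on the assumed shift and correlation, and on no true effect of rating on choice. They run from near nominal with no shift to close to 100% at 0.5 SD and rho 0.3. The calculation shows what the planned reading could produce; it does not show that such a confounder exists or that mediation is absent. A reader might extend the doubt to the main results, but Hypotheses 1 and 3 compare randomised conditions directly and do not use the rating. The plan should be changed on this point, but it does not threaten the primary comparisons.

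**What to change.** In the Analysis Plan, under Statistical models for Hypothesis 2:

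- (a) State that the ACME is causal only if rating and choice share no unmeasured cause within condition and the rating precedes the choice.
- (b) For each ACME, report descriptively a sensitivity analysis over rho, including the value at which the ACME reaches zero. Fit the choice model as a probit so that rho is defined. Attach no pass/fail rule to it.
- (c) State that the rating is collected after the choice, so the choice may drive the rating, and that a large break-even rho does not rule this out.
- (d) In all three places, replace the works-via reading of a significant ACME with: *is consistent with, but does not establish, mediation through the rating*.

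The cost is a small amount of extra analysis on data the study will already hold, and a softer conclusion for Hypothesis 2. No extra participants or questions are needed.

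### The mediation effect read as 'both displays together' (Hypothesis 2) is tied to a total × stratified term whose written coding does not compare condition 4 with condition 1

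*Combined protocol and SAP*

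**What the plan says.** Hypothesis 2 (Hypotheses) predicts that the importance rating for getting any heart is lower in condition 1 than in each of conditions 2, 3 and 4, and that higher ratings go with choosing the non-selective centre. The mediated effect of showing both displays is therefore condition 4 against condition 1.

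The Analysis Plan (Statistical models) introduces the mediation with "The ACME is the effect of each information display condition", listing total, stratified and total × stratified. A significant ACME for the third is interpreted in these words: "the combination of displaying total survival and stratifying transplant survival by number and quality of accepted donors works via increasing the perceived" (that is, the weight put on getting any heart), and so as raising preference for the non-selective hospital. On estimation it says "The unstandardized point estimate of the ACME and its 95% confidence intervals will be interpreted", and for a null result, "If the ACME is non-significant, we will identify where the causal path breaks down".

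Transformations codes the third mediation predictor as "dummy coded (0=total and stratified information not displayed together, 1=both total and stratified information displayed together), with 'both' as the reference category". The stratified predictor is "dummy coded (0=not stratified, 1=stratified), with 'stratified' as the reference category", whereas Manipulated variables names 'combined' as the reference level. The mediator "will be mean-centered for each analysis".

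Only the Hypothesis 1 choice model is given a full specification: "the model will also include an interaction term of these two variables". The plan does not say whether the mediation models keep both main effects, and it does not restrict the third analysis to conditions 1 and 4.

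**The concern.** The third ACME is given the meaning of a simple effect (both displays against baseline), but its variable is an interaction column, or a dummy that places conditions 2 and 3 with the baseline. These quantities can differ in size and in sign.

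The plan's own theory makes this a live issue. Hypothesis 1d expects condition 4 to be no better than condition 2 or 3 on choice, and a negative choice interaction is predicted. If getting any heart drives choice, as Hypothesis 2 claims, the mediator may well show the same sub-additive pattern. The interaction ACME would then be negative although both displays together raise the mediator above baseline. If the displays add, it would be null, and the plan would look for a broken link in a path that is intact. What is at stake is the prespecified conclusion for one part of the mechanism hypothesis.

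**Working it through.** **Inputs.** From the documents: the 0/1 codes (Transformations), the 2×2 layout of conditions 1 to 4 (Study design), about 200 per condition (Sample size), and choice rates of 45% and 60% (Sample size rationale). The documents give no mediator means, SD or slope and state no figure for Hypothesis 2, so there is no planned figure to reproduce. Assumed for illustration: mediator SD 28, log-odds of choice 0.6 per SD, condition 1 choice 45%, no direct effect.

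**Step 1: which contrast the term estimates.** Let M1 to M4 be the mediator means, with equal cells.

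- Target under Hypothesis 2: M4 - M1.
- (a) Main effects kept: M4 - M2 - M3 + M1.
- (b) Dummy alone: M4 - (M1 + M2 + M3)/3.

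Equal pattern (conditions 2 to 4 each 15 above condition 1): target 15; (a) 15 - 15 - 15 + 0 = -15; (b) 15 - (0 + 15 + 15)/3 = 5, one third of the target. Additive pattern (+7.5/+7.5/+15): target 15; (a) 15 - 7.5 - 7.5 + 0 = 0; (b) 15 - (0 + 7.5 + 7.5)/3 = 10.

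**Step 2: combination ACME on the choice scale.** Large-sample values with a linear mediator model, a logit outcome model, and averaging over both exposure levels, in percentage points (simulation error about 0.1):

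| Conditions 2/3/4 above 1 | (a) main effects kept | (b) dummy alone | 4 vs 1 |
|---|---|---|---|
| +15/+15/+15 | -7.3 | +2.4 | +7.4 |
| +10/+10/+15 | -2.5 | +4.1 | +7.4 |
| +7.5/+7.5/+15 | 0.0 | +5.0 | +7.4 |
| +5/+5/+15 | +2.4 | +5.7 | +7.4 |

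For the equal pattern, over shifts of 10 to 20 points and slopes of 0.3 to 0.9 per SD, the ranges are -2.7 to -13.1 for (a), +0.9 to +4.4 for (b), and +2.7 to +13.4 for 4 vs 1.

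**Step 3: at 200 per condition.** Percentile bootstrap of the product of the two path coefficients, 200 resamples (the plan uses 1000), 181 simulated trials for the equal pattern and 164 for the additive.

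- Equal pattern: (a) significantly negative in 98% and positive in 0%; (b) positive in 56% (simulation error about 7 points either way); 4 vs 1 positive in 100%.
- Additive pattern: (a) significant in 6%; 4 vs 1 positive in 100%.

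**Step 4: the total and stratified ACMEs.** These equal 2 vs 1 and 3 vs 1 only if the product is a separate fixed column in a model with main effects. If total is switched inside a true interaction model and averaged over participants, its mediator path is the mean of (M2 - M1) and (M4 - M3). In the equal pattern that is (15 + 0)/2 = 7.5 instead of 15, and the ACME is about +3.7. Entering the total dummy alone gives (M2 + M4)/2 - (M1 + M3)/2 = 15 - 7.5 = 7.5, and an ACME of +3.6, against +7.3 for 2 vs 1. In the additive pattern there is no dilution (+3.7 either way).

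**Step 5: Hypothesis 1d (secondary).** Let b = logit p4 - logit p2 - logit p3 + logit p1 and SE = √Σ[1/(200pq)], two-sided 0.05.

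| Choice in conditions 1/2/3/4 | b | Significantly negative |
|---|---|---|
| 45/60/60/45% (condition 4 equals baseline) | -1.212 | 99% |
| 45/60/60/60% (Hypothesis 1d true) | -0.606 | 56% |
| 45/60/60/65% (condition 4 above 2 and 3) | -0.393 | 27% |

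For the first row, SE = 0.286 and b/SE is about -4.2. Also requiring a significant positive 4-1 contrast cuts 99% to 2.5% but leaves the third row at 27%.

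**The case against.** The best defence is that separate analyses were meant. The ACME is defined for each display condition and the mediator is centred per analysis, so 'total × stratified' may simply be a name for condition 4. If each condition is compared with condition 1, the third bullet is right. That reading has textual support, and it rules out saying that the investigators certainly intend the wrong contrast. It does not rescue the written plan: the 0 category covers every case where the two displays are not shown together, which includes conditions 2 and 3, and no restriction to conditions 1 and 4 appears.

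Other points stand in part. The bullet speaks of increasing importance and increasing preference, so a direction is implied. With the point estimate and interval interpreted, a negative ACME would be seen not to fit. But the trigger is worded as significant or non-significant, and the plan gives no correct reading for a negative value. The search after a null would probably reveal the intact 4 vs 1 shift, which softens the harm.

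The sizes depend on assumptions: Hypothesis 2 does not say that conditions 2 to 4 are equal on the mediator, and the table shows version (a) changing sign across patterns.

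On Hypothesis 1d, the hypothesis is worded as an interaction and the plan tests one. The 45/60/60/45% case would also contradict Hypothesis 1a, which is assigned to the same model, although no bullet states the 4-1 comparison.

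**Conclusion.** The point holds for the coding as written: under neither literal model does the combination term estimate condition 4 versus 1. That is algebra and needs no assumed input. How far the estimate misses depends on unknown mediator means, SD and slope. Under the stated assumptions it runs from the reverse of the target (-7.3 against +7.4 points) through zero to a diluted positive value. This should be fixed before data are seen.

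A reader might infer more than the documents support:

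- **That Hypothesis 2 as a whole is untestable, or that data are lost.** With main effects kept, the 4 vs 1 mediator shift is the sum of three coefficients in the same fit. The total and stratified ACMEs are not necessarily wrong; whether they are 2 vs 1 and 3 vs 1 depends on implementation details that the plan leaves open.
- **That a negative combination ACME is to be expected.** It follows only if the mediator is sub-additive.
- **That the reference labels reverse the results.** 'Stratified' and 'both' are called the reference although each is coded 1, but the numeric codes fix the direction. This is a labelling error.
- **That the choice tests for Hypotheses 1 and 3 are undermined.** The ACME point does not touch them. The separate, secondary point is that a negative interaction is not sufficient for Hypothesis 1d, which also places condition 4 above 1 and not above 2 or 3.

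**What to change.** **Hypothesis 2.** Define the mediation exposure as the four-level condition factor with condition 1 as control, and estimate ACMEs for 2 vs 1, 3 vs 1 and 4 vs 1. Replace the third bullet with the 4 vs 1 ACME and count only a positive ACME as support. If the total × stratified ACME is still reported, label it as an interaction.

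**Transformations (minor).** Correct the reference labels for 'stratified' and 'both' so that they match the 0/1 codes and the reference level named in Manipulated variables.

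**Hypothesis 1d (secondary).** Keep the interaction test, state the 4-1 contrast explicitly, and report 4-2 and 4-3 with 95% confidence intervals. Do not claim 'not higher' from the interaction test alone.

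**Cost.** Plan wording and a few lines of R, with no extra participants and slightly more analysis. Hypothesis 1d becomes harder to support: at 45/60/60/60%, the interaction plus a significant positive 4-1 contrast is met in 48% of trials instead of 56%. The 4-2 interval is also wide: at 60% versus 60% with 200 per condition before exclusions, 1.96 × √(2 × 0.24/200) is about 9.6 points either way. Without a margin, the 4-2 and 4-3 intervals describe the data but give no decision rule for 'not higher'.
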